4.8.2. Adverse Events

Adverse events are to be recorded throughout the study, beginning at the moment of informed consent. AEs will be coded using MedDRA and displayed in tables and listings by SOC and PT.

Analyses of adverse events will be performed for those events that are considered treatment-emergent, where a treatment-emergent AE (TEAE) is defined as one that started, or worsened in severity or seriousness following the first dose of IMP. An AE with onset prior to the start of the administration of the first dose of study drug, or where the stop date is before the start of the administration of the first dose of study drug, or where the study drug injection was not started, will be considered as pre-study. In case the onset date is on the same day as the first dose of study drug and either the time of first dose or time of AE onset is missing, then AE is considered treatment-emergent.

AE intensity will be qualified as mild, moderate, or severe. The relationship to the study drug will be qualified as related (including categories certain, probable/likely, possible) or unrelated.

If the AE start date is missing or partial, the AE will be assigned to the appropriate period using available start date information and the stop date, if present.

Incomplete AE-related dates will be imputed in the following way:

AE start date:

- If the start date of an AE is missing completely, or is partially missing and the month and year or the year are equal to those of the first study drug start date and the AE end date is after or equal to the first study drug start date or missing, then the AE start date will be imputed as the first study drug start date. In case the end date of AE is the same as the IMP start date, non-missing times will also be checked.
- If the AE end date is before the first study drug start date, the AE start date will be imputed as the AE end date if month and/or year is the same.
- Otherwise the month and/or day will be replaced by January and/or 1.

AE end date:

- Incomplete stop dates will be imputed as the last day of the month (if only the day is missing), or the date of death, whichever is earlier.
- In all other cases the incomplete stop date will not be imputed.

Adverse events will be summarised by subject incidence rates, adjusted incidence rates, and number of events. An overview of TEAEs will present the numbers and percentages of subjects experiencing at least one event for the following categories:

- All AEs.
- TEAEs.
- TEAEs by relationship to study drug.
- TEAEs by severity.
- Serious TEAEs.
- Related Serious TEAEs.
- Severe Serious TEAEs.
- TEAEs leading to treatment discontinuation.
- TEAEs leading to study discontinuation.
- All Fatal AEs.
- Fatal TEAEs.
- Related Fatal TEAEs.
- TEAEs leading to hospitalisation.
- TEAEs of clinical interest “CV Death” or “HF Hospitalisation”.
- TEAEs of special interest related to study drug.

Additionally, AEs in the categories listed below will also be summarised by incidence rates and adjusted incidence rates by SOC and PT, as well as number of events (Note: in the descriptive analysis for the incidence rate, each subject will contribute only once to the count for a given SOC or Preferred Term, regardless of the number of episodes experienced):

- TEAEs.
- TEAEs related to study drug.
- TEAEs by relationship (without adjusted incidence rates).
- Severe TEAEs.
- TEAEs by severity (without adjusted incidence rates).
- Serious TEAEs.
- Serious TEAEs occurring in > 5 % of the subjects.
- Non-serious TEAEs.
- Serious TEAEs related to study drug.
- TEAEs leading to treatment discontinuation, “drug withdrawn” in the eCRF.
- TEAEs leading to study discontinuation.
- Serious TEAEs by severity,
- Fatal TEAEs,
- Fatal TEAEs related to study drug,
- TEAEs of clinical interest (by PT only),
- TEAEs of special interest (by PT only) related to study drug.

Adjusted incidence rate will be calculated by dividing the number of subjects with a particular TEAE by the subject-years of time on study (see section 4.2.14) of all subjects in each treatment group.

In the tabulations by severity or relationship, each subject will contribute only once to each of the incidence rates by using the worst severity/strongest relationship reported within the period of interest; all events experienced will be counted in the event rates.

If the relationship is missing, the AE will be considered related to study drug. If the severity is missing, the AE will be considered to be severe.

Cardiovascular AE terms of clinical interest as reported by Investigators will be listed in this order in the table:

1. CV death
2. HF hospitalisation

The CV AEs of clinical interest as reported by Investigators will be identified as follows:

1. For HF hospitalisations: PT = “Cardiac failure”, “Cardiac failure acute”, “Cardiac failure congestive”. or “Cardiac failure chronic” and led to or prolonged hospitalisation = Yes
2. For CV death: SOC = “Cardiac Disorders” and results in death = Yes, and PT=”Sudden cardiac death” in SOC “General disorders and administration site conditions”

AEs of special interest include “hypersensitivity reactions”, “hypophosphatemia”, “injection/infusion site reactions” and “haemosiderosis”. Only events related to study drug are considered. Each category will be identified as follows:

1. Hypersensitivity reactions: PT = “Hypersensitivity”, “Anaphylactic reaction”, “Anaphylactic shock”, “Anaphylactoid shock” or “Anaphylactoid reaction”
2. Hypophosphatemia: PT = “Blood phosphorus decreased”, “Blood phosphorus abnormal”, “Hypophosphataemia”, “Hypophosphataemic osteomalacia” or “Hereditary hypophosphataemic rickets”
3. Injection/infusion site reactions: HLT = “Infusion site reaction”, “Injection site reactions”, “Administration site reactions NEC” or “Infusion related reaction”
4. Haemosiderosis: PT = “Haemosiderosis”, “Haemeatochromatosis”, “Iron overload”, “Hepatic siderosis”, “Cardiac iron overload”, “Pulmonary haemosiderosis” or “Superficial siderosis of central nervous system”

A listing of pre-study AEs and listing of AEs starting between randomisation date and start of treatment will be presented. All TEAEs occurring on study will be listed in subject data listings, as will related TEAEs, SAEs, related SAES, TEAEs leading to study drug discontinuation or death. Data will not be imputed in the listings.

Relevant pregnancy information captured in the eCRF will be listed.

All deaths details will be listed.

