The study treatment doses administered at Visits 2 and 3 are considered as the “repletion phase” and any subsequent administrations (if ID persists) will be considered as the “maintenance phase”. The first dose of study treatment will be administered for all randomised subjects at Visit 2 while the subject is still hospitalised for the Index hospitalisation. It is recommended that the first dose of study treatment is administered on the same day as randomisation. To accommodate local hospital practice, the first dose of study treatment may be administered either on the same day or the day before the planned discharge day. Note that a planned overnight stay following study treatment administration does NOT fulfil the criteria of a serious adverse event (SAE) unless there is a medical reason for doing this. The subsequent administrations of study treatment will be done as part of the outpatient clinic visits at Week 6 (Visit 3), and at Weeks 12 (Visit 4) and 24 (Visit 5). Dosing at Week 6 (Visit 3) will be based on the iron need upon screening Hb and weight values to replete iron as described in Table 1 and only be done in subjects for whom Hb at Week 6 (Visit 3) ≤15 g/dL. Maintenance dosing at Weeks 12 (Visit 4) and 24 (Visit 5) is only for subjects in whom ID persists and for whom Hb ≥8 g/dL* and ≤15 g/dL at those visits. ID is defined as serum ferritin <100 ng/mL, or 100 ng/mL ≤ serum ferritin ≤299 ng/mL if transferrin saturation (TSAT) <20%. The serum pregnancy test must also be negative for the respective visit for females of childbearing potential. Subjects will be requested to return to the outpatient clinic for the administration of study treatment maximally 7 days after the date when the blood sample was drawn.

Study treatment will be prepared by an unblinded study personnel using black syringes and once prepared, study treatment should be administered immediately thereafter using a curtain (or similar) to maintain subject blinding. Each subject should be observed for adverse effects for at least 30 minutes following each injection of study treatment. The unblinded study personnel may be involved in performing screening activities. Following randomisation the unblinded study personnel will not be operationally involved in the study for the subject concerned other than the preparation and administration of study treatment and assessment and interpretation of post-randomisation laboratory test results.

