10.2.4 Pre-existing Medical Conditions

A pre-existing medical condition is one that is present at the screening visit for this study. Such conditions should be recorded on the medical history eCRF. A pre-existing medical condition should be recorded as an AE only if the frequency, severity, or character of the condition worsens during the study. When recording such events on the AE eCRF, it is important to convey the concept that the pre-existing condition has changed by including applicable descriptors (e.g., “more frequent headaches”).

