		16.2.6.4.1 Events Adjudicated by Clinical Endpoint Committee – Full Analysis Set
		16.2.6.4.2 Events Adjudicated by Individual Adjudicators – Full Analysis Set
		16.2.6.5 Hospitalisation Details – Full Analysis Set
		16.2.6.6 NYHA Functional Class – Full Analysis Set
		16.2.7.1 All Adverse Events – Safety Analysis Set

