		16.2.7.2 Serious Adverse Events – Safety Analysis Set
		16.2.7.3 Adverse Events Leading to Study Product Discontinuation – Safety Analysis Set
		16.2.7.4 Death Details – Safety Analysis Set
		16.2.7.5 Hypersensitivity Reactions – Safety Analysis Set
		16.2.7.6 Non-Treatment Emergent Adverse Events – Safety Analysis Set

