		16.2.7.7 Adverse Events between Randomisation and Start of Treatment – Safety Analysis Set
		16.2.8.1 Local Laboratory Results – Safety Analysis Set

Type*	Section	Title

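### SAP 4.8.2 makes an adverse event that starts before the first dose and worsens after it both treatment-emergent and pre-study

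*SAP*

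**What the plan says.** SAP 4.8.2 (Adverse Events) limits the adverse event analyses to treatment-emergent events and defines these as events that "started, or worsened in severity or seriousness following the first dose of IMP". Worsening after dosing is therefore enough, whatever the date of onset.

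The following sentence sets out what is pre-study. It gives three alternative conditions joined by *or*. The first is "An AE with onset prior to the start of the administration of the first dose of study drug"; the others are a stop date before that dose, and an injection that was never started. Meeting any one of them suffices.

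Later in the same section the SAP plans two listings: "A listing of pre-study AEs and listing of AEs starting between randomisation date and start of treatment will be presented". The output list in SAP 7.1 contains "16.2.7.6 Non-Treatment Emergent Adverse Events" and "16.2.7.7 Adverse Events between Randomisation and Start of Treatment". It has no listing with pre-study in its title.

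**The concern.** The two sentences give opposite answers for an event that is already present when the first dose is given and then gets worse. If a programmer follows the definition, it goes into the TEAE tables. If the programmer follows the pre-study sentence, it does not. The second route is the easier one to code, because it needs only the onset date.

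What would be lost is a group of events that, by construction, all deteriorated after study drug. They are the reason the worsening limb was put into the TEAE definition, and the pre-study sentence would leave that limb without effect for them.

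**Working it through.** The plan gives no figure to reproduce. The check is to apply both rules to one record and then look for anything in the documents that settles the result.

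**Test case.** An event starts after consent and before the first dose, is moderate at that point, continues, and is severe after the dose.

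- TEAE definition (SAP 4.8.2): worsened in severity after the dose, so treatment-emergent.
- Pre-study sentence (SAP 4.8.2): onset before the dose, so pre-study. The other two conditions need not be met.

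**Does another SAP rule decide it?** The third sentence of that paragraph handles only onset on the dosing day with a missing time. SAP 4.2.12 likewise deals only with missing times on the day of first dose. I found no order of precedence.

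**Does the way events are recorded remove the case?** Collection starts at consent, so pre-dose onsets do reach the database. Under Protocol 10.3.1 an event that continues without resolving has a single record, and its severity is updated on that record. It therefore keeps its pre-dose onset date, and no new post-dose record is created.

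**Are the two labels meant to exclude each other?** The two listings planned in the text of 4.8.2 correspond, in order, to 16.2.7.6 and 16.2.7.7. The pre-study listing is therefore the one titled "16.2.7.6 Non-Treatment Emergent Adverse Events". On that match, pre-study is used to mean not treatment-emergent.

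**Which events are affected?** Several protocol rules narrow the class.

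- Protocol 10.2.4: "A pre-existing medical condition is one that is present at the screening visit for this study". Such a condition becomes an adverse event only when it worsens, so the conflict concerns events new after screening.
- Protocol 10.2.5: heart failure signs and symptoms are recorded as adverse events when they worsen.
- Protocol 10.3.2: a serious event is dated from when it became serious, so worsening in seriousness after the dose gives a post-dose onset.
- Protocol synopsis, Treatment: the first dose is given "while the subject is still hospitalised for the Index hospitalisation", which keeps the window short.

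What remains is a non-serious event, new between the screening visit and the in-hospital first dose, still ongoing at that dose, and later worse in severity.

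**Scale.** Input: 550 subjects planned per arm (SAP 4.1). If an affected subject has no other event of the same preferred term, the change in that term's TEAE incidence in that arm is

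1 / 550 = 0.0018 = 0.18 percentage points.

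This is per affected subject and is not an estimate of the total. The number of affected subjects cannot be derived from the documents. The actual denominator will be the Safety Set, which counts dosed subjects by treatment received and may differ somewhat from 550.

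**The case against.** The strongest reply is that the TEAE definition is explicit and the safety tables in SAP 7.1 are specified by TEAE status, never by pre-study status. A careful programmer would apply the definition and keep the event, so omission is only one reading. The match between the pre-study listing and 16.2.7.6 is also an inference. Its title could equally mean that listings are sorted by TEAE status, in which case a worsened event would simply not appear there.

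It is fair to say that omission depends on which sentence is coded, and no omission has been shown. The reply still needs the pre-study sentence to be disregarded for these events, which concedes that it is wrong as written. Both sentences cannot be followed for the same record.

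A second reply is that the amendment may change no table. Protocol 10.3.1 asks for worst intensity and an updated severity, with no date of worsening. If the data cannot show when an event worsened, the added clause cannot be applied to it, and a flag in a listing leaves the tables as they were. That limit is real. The eCRF is not among the documents, so whether the timing is held cannot be settled here.

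A third reply is that the effect is tiny, the rule is the same in both arms, and safety is descriptive. All of this stands and sets the severity. An affected event would also remain visible in the all-AE overview row and in "16.2.7.1 All Adverse Events". It would appear in 16.2.7.6 if that is the pre-study listing, in 16.2.7.7 if it began between randomisation and dosing, and in 16.2.7.3 if it led to discontinuation of study drug.

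**Conclusion.** The concern holds, as a minor one. Two consecutive sentences of SAP 4.8.2 contradict each other for an event that starts before the first dose and worsens in severity after it, and nothing else in the SAP or protocol resolves the conflict. Applied as written, the pre-study sentence would give a TEAE count that departs from the SAP's own definition.

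The practical effect is expected to be small: 0.18 percentage points on one preferred term for each affected subject, with an unknown but probably low number of subjects. This assumes the protocol's recording rules are followed and that the pre-study sentence is the one coded. No efficacy conclusion changes.

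**What to change.** In the pre-study sentence of SAP 4.8.2, qualify the first condition only. After "An AE with onset prior to the start of the administration of the first dose of study drug", insert: *and which did not worsen in severity or seriousness after the first dose*. Leave the other two conditions as they are.

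Before programming, confirm whether the eCRF or its audit trail dates a change in severity. If it does not, add a column to listing 16.2.7.6 marking events ongoing at the first dose, and do not impute them as TEAEs. That fallback would not alter the tables, but it lets a reader see which events are in doubt.

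The cost is one clause and, at most, one column in a listing already planned. It needs no new data and leaves every efficacy analysis unchanged.

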Since the developmental international birth date, more than 7,000 subjects are known to have been exposed to FCM with at least one dose in more than 35 completed prospective, interventional clinical studies. Across various clinical studies, replenishment of iron stores has been consistently observed. Markers of ID have included both TSAT and serum ferritin. In subjects with more severe or prolonged ID that has led to anaemia, correction of ID using FCM has consistently resulted in medically significant increases in haemoglobin (Hb) values (correction of anaemia). This improvement was usually seen within 2 weeks. In addition to the correction of laboratory parameters, iron replacement therapy has demonstrated significant improvements in subject QoL and functional status. Ferric carboxymaltose was well tolerated by study participants. In the completed clinical studies, up until the 1 January 2015, approximately 50% of the subjects experienced at least 1 treatment-emergent adverse event (AE), and events considered related to treatment occurred in just over 17% of subjects who received FCM. The most commonly reported adverse drug reactions (ADRs) in the FCM group were nausea, injection/infusion site reactions, hypophosphataemia, headache, flushing, dizziness, and hypertension.

In relation to laboratory parameters recorded in clinical studies, no consistent pattern of clinically meaningful changes requiring intervention have been observed. However, mild and transient changes of liver enzymes, such as aspartate aminotransferase and alanine aminotransferase, gamma-glutamyl transferase and alkaline phosphatase, have been reported in some studies. A transient decrease in blood phosphorus levels was frequently observed. The nadir occurred approximately 2 weeks after dosing and resolved without treatment in most subjects within the follow-up period of up to 12 weeks. Severe hypophosphataemia (i.e., <0.3 mmol/L) was observed in very few cases, and was of short duration.

No formal interaction studies have been performed. Except for the reduced uptake of oral iron administered in parallel with parenteral iron, no interactions with other medications are known.

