2.5.4. Safety Endpoints

- Incidence of adverse events (AEs): by System Organ Class (SOC) and Preferred Term (PT) (Medical Dictionary for Regulatory Activities (MedDRA) coded term), by maximum severity, related to study drug, leading to study drug discontinuation, serious, leading to death, and adjudicated.
- Incidence of AEs of clinical interest: HF hospitalisation and CV death.
- Incidence of Special Situation Events.
- Incidence of event adjudication (Hospitalisation, Urgent HF visit and Deaths).
- Incidence of related AEs of special interest: Hypersensitivity reactions, Hypophosphatemia, Injection/infusion site reactions and Haemosiderosis.
- Clinical laboratory panels (absolute and change from baseline, incidence of laboratory abnormalities).
- Vital Signs (absolute and change from baseline).
- Electrocardiograms (incidence of electrocardiogram abnormalities, QTc measurement meeting ICH E14 criteria [2]).
- Prior, concomitant and newly started medications.

Note: biomarkers exploratory analyses will not be part of the CSR of the main study. They will be described in a separate biomarker SAP.

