4.8.1. Treatment Exposure and Compliance

Time on study (follow-up) in weeks and subject-years on study as defined in sections 4.2.14 and 4.2.18 will be summarised as continuous variables. Time on study drug as defined in section 4.2.15 will also be summarised.

Treatment Exposure

The number of injections of study drug per subject will be summarised as a categorical variable (1, 2, 3, 4). The total amount of study drug given and planned (see Table 6 and Table 7) across

visits (mL) will be calculated for each subject, and will be summarised by treatment group. Summary statistics for the doses received (in mL and in mg) at each visit be also presented.

The total amount of study drug and the doses received at each visit in mL and mg will also be summarised as a continuous variable.

Treatment Compliance

The planned dose will be derived based on the protocol number, protocol consent and re-consent dates, serum pregnancy test result, weight, Hb levels, and ID status as per Table 6 and Table 7 below. Table 7 will apply only for subjects who consented to protocol 2 or 3 or if the subject re-consented to protocol 2 and the injection date is on or after the protocol re-consent date. ID is defined as serum ferritin <100 ng/mL, or $100 \text{ ng/mL} \leq \text{serum ferritin} \leq 299 \text{ ng/mL}$ if transferrin saturation (TSAT) is <20%. The laboratory and vital sign values closest to the injection date and time (\leq) will be used. In case no injection was done, the value closest to the visit date will be used.

For the protocol 1, the first dose of study treatment is administered for all randomised subjects on the same day as randomisation – i.e., at Visit 2 while the subject is still hospitalised for the Index hospitalisation. The subsequent administrations of study treatment are done as part of the outpatient clinic visits at Week 6 (Visit 3), and at Weeks 12 (Visit 4) and 24 (Visit 5) only for subjects in whom ID persists and for whom $\text{Hb} \geq 8 \text{ g/dL}$ and $\leq 15 \text{ g/dL}$. The serum pregnancy test must also be negative for the respective visit for females of childbearing potential.

The dosing regimen for protocol 1.2 is similar to the one from protocol 1 except for the subjects from The Netherlands (NL). For NL subjects, the lower threshold of Hb values is set to 10 g/dL.

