For the protocol 2 and 3, dosing at Week 6 (Visit 3) is based on the iron need upon screening Hb and weight values to replete iron as described in Table 7 and only be done in subjects for whom $\text{Hb} \leq 15 \text{ g/dL}$. Maintenance dosing at Weeks 12 (Visit 4) and 24 (Visit 5) is only for subjects in whom ID persists and for whom $\text{Hb} \geq 8 \text{ g/dL}^*$ and $\leq 15 \text{ g/dL}$ at those visits. The serum pregnancy test must also be negative for the respective visit for females of childbearing potential.

* Following section in italics is applicable for The Netherlands, Spain and Singapore only (**NL, ES and SG only**):

The lower threshold of Hb values is set to 10 g/dL.

Table 6 Study drug Dosing Regimen Protocol 1

Treatment Visit	Total mL FCM or Saline				
	Weight <70 kg		Weight ≥70 kg		Any Weight
	8 g/dL ≤ Hb < 10 g/dL	10 g/dL ≤ Hb ≤ 14 g/dL	8 g/dL ≤ Hb < 10 g/dL	10 g/dL ≤ Hb ≤ 14 g/dL	
Visit 2 (Week 0)	2x10 mL				1x10 mL
Visit 3 (Week 6)	1x10 mL (only if ID persists)	No dose	2x10 mL (only if ID persists)	1x10 mL (only if ID persists)	No dose
Visit 4, Visit 5 (Week 12, Week 24)	1x10 mL (only if ID persists)				

Notes: FCM=Ferric carboxymaltose; Hb=Haemoglobin; ID=Iron deficiency.

Table 7 Study drug Dosing Regimen Protocols 2, 3

Treatment Visit	Total mL FCM or Saline				
	Weight <70 kg		Weight ≥70 kg		Any Weight
	8 g/dL ⁽¹⁾ ≤ Hb <10 g/dL	10 g/dL ≤ Hb ≤14 g/dL	8 g/dL ⁽¹⁾ ≤ Hb <10 g/dL	10 g/dL ≤ Hb ≤14 g/dL	
Visit 2 (Week 0)	2x10 mL				1x10 mL
Visit 3 ⁽²⁾ (Week 6)	1x10 mL	No dose	2x10 mL	1x10 mL	No dose
Visit 4, Visit 5 (Week 12, Week 24)	1x10 mL (only if ID persists)				

1 Following section in italics is applicable for The Netherlands, Spain and Singapore only (NL, ES and SG only): *The lower threshold of Hb values for subject eligibility prior to enrolment into the study is set to 10 g/dL. Subjects enrolled in the study in NL, ES and SG only with Hb levels that are falling below the threshold of 10 g/dL during the study will need to be withdrawn from further study treatment dosing.*

2 Dosing at Week 6 (Visit 3) will be based on the iron need upon screening Hb and weight values and only be done in subjects for whom Hb at Week 6 (Visit 3) ≤15 g/dL.

Notes: FCM=Ferric carboxymaltose; Hb=Haemoglobin; ID=Iron deficiency.

The algorithm to calculate the planned dose is described in Appendix II.

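### Dosing that depends on persistent iron deficiency should give placebo subjects more injections, and the planned reaction tables do not allow for it, so a modest per-injection excess with FCM can be diluted or masked

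*SAP*

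**What the plan says.** **Dosing.** The Protocol synopsis (Treatment) states: "Maintenance dosing at Weeks 12 (Visit 4) and 24 (Visit 5) is only for subjects in whom ID persists". The same rule applies in both arms. Week 6 differs by protocol version. Under protocol 1 (SAP Table 6) every scheduled Week 6 dose is also conditional on ID, for example "1x10 mL (only if ID persists". Under protocols 2 and 3 (SAP Table 7), "Dosing at Week 6 (Visit 3) will be based on the iron need upon screening Hb and weight values", and the dose is withheld if Week 6 Hb is above 15 g/dL or a pregnancy test is positive.

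**Expected effect on iron.** Protocol 1.2 reports of FCM: "Across various clinical studies, replenishment of iron stores has been consistently observed". The placebo is normal saline (Protocol 7.1.2).

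**Safety summaries.** SAP 2.5.4 lists "Incidence of related AEs of special interest: Hypersensitivity reactions, Hypophosphatemia, Injection/infusion site reactions and Haemosiderosis". SAP 4.8.2 restricts these to events judged related and plans three measures: "Adverse events will be summarised by subject incidence rates, adjusted incidence rates, and number of events". On the second: "Adjusted incidence rate will be calculated by dividing the number of subjects with a particular TEAE by the subject-years of time on study". No reaction table is split by dosing visit, limited to a period after an injection, or divided by injections given.

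**Exposure.** SAP 4.8.1 states: "The number of injections of study drug per subject will be summarised as a categorical variable (1, 2, 3, 4". Doses received at each visit are also tabulated, and dosing and hypersensitivity reactions are listed by subject.

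**The concern.** An injection-site or acute hypersensitivity reaction needs an injection. Both arms have the same venous puncture, catheter and flush (Protocol 7.2.2.2), so placebo also carries some background risk each time. If placebo subjects are injected more often, they have more opportunities for an event, and the comparison per subject is pulled towards FCM looking safer.

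The adjusted rate does not correct this. Its denominator is time on study, which follow-up makes roughly equal between arms and which SAP 4.2.14 caps at 375 days. The last scheduled injection is at Week 24 (day 168). For a subject followed to the cap, (375 - 168)/375 = 55% of the denominator comes after the last scheduled injection. Raw event counts are not divided by injections either.

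Tolerability and safety is a stated secondary objective, and Protocol 8.1 treats hypersensitivity to parenteral iron as potentially fatal. The direction of any understatement can be foreseen from the design.

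**Working it through.** **The plan's own figure.** There is none to reproduce. The documents give no expected injections per arm, no rate of persistent ID by arm and no reaction rate per injection. All rates below are assumptions for illustration.

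**Step 1: mean injections per subject.** Everyone in the Safety Set has the Visit 2 injection. With w the share dosed at Week 6 (taken as equal between arms, as under protocols 2 and 3) and q the proportion with persistent ID at Weeks 12 and 24:

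m = 1 + w + 2q

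Base case: w = 0.5, q = 0.30 (FCM) and 0.80 (placebo).
- FCM: 1 + 0.5 + 0.6 = 2.1
- Placebo: 1 + 0.5 + 1.6 = 3.1

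**Step 2: per-subject ratio when the risk per injection is equal.** With risk p per injection, P(at least one reaction) = 1 - (1 - p)^m. At p = 1%:

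(1 - 0.99^2.1)/(1 - 0.99^3.1) = 0.0209/0.0307 = 0.68

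The true per-injection ratio that would read as about 1.0 is 3.1/2.1 = 1.48.

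**Step 3: range.** For rare events the multiplier is close to the ratio of mean injections.

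| Assumptions | FCM / placebo injections | Multiplier | Per-injection ratio that reads as 1.0 |
|---|---|---|---|
| w 0.3, q 0.2 vs 0.8 | 1.7 / 2.9 | 0.59 | 1.71 |
| Base case | 2.1 / 3.1 | 0.68 | 1.48 |
| w 0.7, q 0.4 vs 0.7 | 2.5 / 3.1 | 0.81 | 1.24 |

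The first and last rows are the extremes for w 0.3-0.7, FCM q 0.2-0.4 and placebo q 0.7-0.8. A wider set (w 0.4-0.8, FCM q 0.1-0.3, placebo q 0.5-0.9) gives multipliers from 1.6/3.2 = 0.50 to 2.4/2.8 = 0.86. All lie below 1.

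**Step 4: what still shows.** Take 2.0 FCM and 3.0 placebo injections, a placebo risk of 0.5% per injection and 550 subjects per arm. Placebo subjects with an event: 550 x (1 - 0.995^3) = 8.2.

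| True per-injection ratio | FCM subjects with an event | Per-subject ratio |
|---|---|---|
| 1.5 | 8.2 | 1.00 |
| 2 | 10.9 | 1.33 |
| 3 | 16.4 | 1.99 |
| 5 | 27.2 | 3.31 |

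A ratio of 1.5 disappears. Ratios of 3 and 5 are diluted but visible.

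**Step 5: what the added displays would show at a true ratio of 1.5.**
- Per injection: FCM has 550 x 2.0 = 1,100 injections and 1,100 x 0.75% = 8.25 expected reactions. Placebo has 550 x 3.0 = 1,650 injections and 1,650 x 0.5% = 8.25. Dividing by injections gives 0.75% against 0.50% and recovers 1.5.
- Visit 2 only: 550 x 0.75% = 4.1 against 550 x 0.5% = 2.75 expected reactions. Exposure is equal but events are few.

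**The case against.** **The planned measure is legitimate.** Risk per treated subject describes what happens under each dosing strategy, and fewer injections are part of the FCM strategy. Safety data are descriptive and SAP 4.8.2 plans no test. This stands, so the per-subject tables are not wrong and should not be displaced.

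**The ingredients are there.** Event counts and injections per subject are both tabulated, so a reader can form a crude rate per injection. This stands in part. A comparison after the first injection, or by dosing visit, cannot be read from any planned summary table. It would need dosing and AE listings to be matched by hand.

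**The size is unknown.** This stands. Several rules also change injection counts: the Hb limits, withdrawal from dosing below 10 g/dL in the Netherlands, Spain and Singapore (Protocol 5.4.1), and stopping for restricted treatments (Protocol 7.7.2). Some of these could fall more on placebo and narrow the gap. Masking also needs a saline reaction rate fairly close to that of FCM, and the documents describe these reactions as risks of parenteral iron.

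**A stronger reading.** A reader might infer that the plan hides an FCM excess, or that the tolerability objective as a whole is biased. The documents do not support either. The multiplier rests on assumed rates, a large excess would still show, and only two of the four special-interest categories are treated here as tied to the injection. A reader might also want the first-injection comparison as the main one. That goes too far: Protocol 8.1 warns that reactions can follow earlier uneventful doses, so a Visit 2 table alone would miss relevant events.

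**Conclusion.** The point holds as a gap in the planned safety displays. The dosing rules and the expected effect of FCM on iron stores make more injections on placebo likely, and none of the three AE measures allows for it. The effect is towards understating an FCM excess in related hypersensitivity and injection/infusion-site reactions.

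Illustratively, the per-subject ratio is the per-injection ratio multiplied by about 0.6-0.8 (0.50-0.86 over the wider assumptions), so a modest excess, around 1.2 to 1.7, could read as no difference. This depends on persistence rates that the documents do not give, on equal Week 6 dosing between arms, and on a constant risk per injection. Under protocols 2 and 3 the imbalance comes mainly from Weeks 12 and 24. Under protocol 1, Week 6 can add to it.

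**What to change.** Keep the per-subject tables in SAP 4.8.2 as planned. For related hypersensitivity reactions and injection/infusion-site reactions only, add two supplementary descriptive displays by arm on the Safety Set:

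1. **First injection.** Reactions with onset on the day of the Visit 2 injection, or within a short window after it. Fix the window length before unblinding; the documents do not supply one. Every Safety Set subject has exactly one injection at this visit, so exposure is equal and precedes any dosing that depends on response.
2. **By dosing visit and per injection.** Reactions in the same window after each injection, shown by visit and divided by the number of injections given. Add a footnote that the number of later injections depends on treatment and on earlier reactions, since a hypersensitivity reaction stops study drug and further doses are decided case by case (Protocol 5.4.1). This rate is therefore not a purely randomised comparison.

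Administrations and AE onset dates are already recorded in the eCRF (Protocol 7.2.2 and 10.3.1). No new data and no change to dosing are needed. The cost is two small tables, and the first-injection table will hold few events and should be read as descriptive.
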